## **6.5 Placebo Administration**

A wound area is selected to serve as the control at baseline. Topical placebo is administered on the days in which KB103 is administered. If KB103 is not administered to both of the KB103-selected wound areas on any dosing day, then placebo will not be administered. The dressings applied to the wound area that is administered the placebo gel mimic those applied to wound area administered KB103.

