## 1.6 Rationale for Protocol Amendments

Four subjects were enrolled onto version 2 of the Phase 2 portion of the protocol. Three subjects (1 adult and 2 children) were administered 3e8 per wound daily for 5 days. One adult was administered 6e8 daily for 5 days. There were no signs of immunogenicity, no KB103-related adverse events and the data indicate that 3e8 per wound per administration was an effective dose for wounds 20 cm^2 or less.

Post-dose imaging from these patients clearly indicated that wound morphology and size is a major factor in wound healing as a result of KB103 administration. Wounds that were chronic but recurring based on natural history tended to heal and close completely within 7 to 10 days of KB103 administration. Chronic wounds that were open for a few years showed signs of healing following an initial five consecutive applications but the wound healing process appears to stagnate. These wounds would likely benefit from additional administrations to obtain full closure. Caregivers of the patients currently on trial have requested additional administrations to wounds that have clearly benefited but have not achieved complete wound closure.

Therefore, version 3.1 of the protocol incorporated dosing every 2 to 3 days for two weeks at 2e8 PFU with the option of at-home KB103 administrations, at the discretion of the Investigator.

Five patients were enrolled onto version 3.1 of the protocol. KB103 continues to be well tolerated and wound healing is observed in KB103 administered wounds. Wound healing results of the KB103 treated wounds evaluated to-date continues to show improvement. There is also empirical evidence that repeat administration on the chronic wounds that were retreated in patients that rolled over from the previous portion of the study showed improved healing with complete closure of the wound observed. Therefore, version 4.0 incorporates a 2-cycle approach to KB103 administration with greater flexibility given regarding the number of administrations within each cycle to understand the duration of treatment prior to moving into the Phase 3 Clinical trial.

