### **6.1      At-Home Topical Administrations**

At the discretion of the Investigator, KB103 may be administered at home. The Investigator will use at-home imaging to make remote dosing decisions, for example, if at-home dosing should discontinue due to wound closure.

Trained caretakers may administer KB103 or trained personnel may travel to the subject to administer KB103. Training will be documented and will consist of administration, containment, and disposal procedures. At-home administration and disposal instructions are provided to the subjects and are in Appendix 1.

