## 6.4 KB103 Administration

At-home topical administration of KB103 and placebo is performed as outlined in Appendix 1.

KB103 will be administered only if a target wound is visibly open. An opening as the result of biopsy will be considered visibly open wound. KB103 is compounded into a gel per the pharmacy manual.

On-site administration is performed as follows:

1. Unpackage the Mepitel One, Mepiform, Vaseline, and Kerlix Gauze dressings and place them nearby. Prepare the wound for KB103 administration by unbandaging the area. Cut a hole in the Mepitel One to the size of the wound to be treated and place the cut Mepitel on the patient's skin around the wound surface.
2. To apply KB103, while wearing gloves, apply the compounded product directly to the patient's skin by depressing the syringe plunger very slowly to cover the surface of the wound with KB103. Ensure that the KB103 is contained to the wound without any spillage.
3. If necessary, open a new syringe, connect the spreader and use it to spread the product on the patient's skin.
  - a. Any spillage on hard surfaces should be immediately wiped up with 10% bleach wipes, and any used wipes should be disposed of as a biohazard per standard operating procedure of the clinical site.
4. Let the KB103 sit for 5 minutes prior to placing any covering over the wound. Keep the area clean and do not touch the wound during the 5-minute period.
5. After applying KB103, remove the gloves, discard them in the biohazard container, and put on a new pair of gloves.
6. Cover the wound using the non-adherent side of the Mepiform above the wound and then cut to the full size of Mepitel dressings.

7. Thoroughly wrap the dressing in Vaseline Kerlix Gauze and further dress per standard of care.

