## 14 Appendix 1 – KB103 Administration and Removal Instructions

### At-Home Administration Instructions

1. Open the compounding, dressing, cleaning and handling kits.
2. Put on the gloves provided with the cleaning and handling kit.
3. You will receive two KB103 vials for each wound to be treated. The vials are shipped on dry ice and stored in an ultra-low temperature freezer at the patient's home. Open the ultra-low temperature freezer and remove four KB103 vials. Inspect the vials for signs of leakage. If leakage as occurred, take a picture of the leakage and dispose of the vial in the provided red biohazard bag.
4. Place the KB103 vials on the blue towel provided in the cleaning and handling kit and let them sit for 20 to 30 minutes to allow the KB103 to warm to room temperature. **Do not let the vials sit for more than 40 minutes prior to use.**
5. The study team will tell you which of the wounds should be given KB103. If you are unsure, contact your study doctor or study coordinator.
6. Unpackage Mepitel One, Mepiform, Vaseline, and Kerlix Gauze dressings that were provided with the dressing kit and place them nearby. Prepare the wound for KB103 administration by unbandaging the area. Cut a hole in Mepitel One to the size of the wound to be treated and place the cut Mepitel on the patient's skin around the wound surface.
7. To compound KB103 with the gel, take one syringe and attached an 18G needle to it. Open a vial of KB103 and draw the product entirely into the syringe (each vial contains 200uL of KB103). Repeat the same procedure to draw the same volume of gel into a second syringe.
8. Activate safety cover of the needles and removes needles from syringes. Discard the needles in the sharp needle's container.
9. Join the two syringes using the guarded Luer lock connector.
10. To mix KB103 and gel (1:1 dilution), place the syringes in a vertical position and keep the syringe containing KB103 on top. Slowly dispense the syringe containing KB103 while drawing on the syringe containing the gel until all KB103 is mixed with the gel. Invert the syringes and repeat this operation twice.

11. Disconnect the syringes, keep the syringe containing the compounded product and apply directly to the patient's skin depressing the syringe plunger very slowly to cover the surface of the wound with KB103. Ensure that the KB103 is contained to the wound without any spillage.  

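### Section 6.5 sets placebo dosing by the state of the KB103 areas and ignores the control wound, so on the more natural reading an open control can stop receiving vehicle because another wound has closed

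*Protocol*

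**What the plan says.** Two sentences in Protocol 6.5 govern vehicle. The first is "Topical placebo is administered on the days in which KB103 is administered". The second is "If KB103 is not administered to both of the KB103-selected wound areas on any dosing day, then placebo will not be administered". Neither mentions whether the control wound is open or closed.

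KB103 dosing itself depends on closure. Section 6.4 states: "KB103 will be administered only if a target wound is visibly open". Section 6.1 states: "The Investigator will use at-home imaging to make remote dosing decisions, for example, if at-home dosing should discontinue due to wound closure". Step 5 of the at-home instructions in Appendix 1 shows that KB103 is assigned wound by wound: "The study team will tell you which of the wounds should be given KB103".

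Other sections leave gaps:

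- **Whose closure ends dosing.** Sections 4.1 and 6 end dosing at closure or at three months per cycle but do not identify the wound.
- **What restarts dosing.** Section 4.1 starts Cycle 2 when a wound in the KB103 area re-opens or expands. Section 5.5 ends OP 1 on re-opening, or on an increase in area, without naming the area.
- **OP 2 visits.** Section 5.7.1 gives both products at a monthly visit if a target wound is open.
- **Number of KB103 areas.** Section 6.3 first selects one KB103 and one placebo area. A second KB103 area is optional.
- **Placebo at home.** Section 6.4 says "At-home topical administration of KB103 and placebo is performed as outlined in Appendix 1", but Appendix 1 has no placebo step.

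**The concern.** In a within-subject comparison, both wounds should be treated under the same rule, so that under no drug effect they have the same expected course. Section 6.5 breaks this. A KB103 area is treated until it closes, whereas the control is treated until a different wound closes. That holds even if KB103 is no better than its vehicle. If the KB103 wound closes first, the control loses its gel. If the control closes first, the KB103 wound keeps its product.

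Time to closure against placebo is a primary objective (Protocol 2.1). The SAP compares healing at Weeks 8, 10 and 12 (8.1.1) and mean closure times by analysis of variance (8.1.2). If the gel helps healing, withholding it from open controls lowers the placebo healing proportion, lengthens placebo closure times and so favours KB103.

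The planned SAP summaries would not show it. Compliance in SAP 7.3 divides doses received by doses expected between the first and last dose dates, so a control stopped in the second week could still be reported as fully compliant.

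**Working it through.** The documents give no figure for this point, so there is nothing to reproduce. The check has two parts.

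**1. What 6.5 does in each state.** Take two KB103 areas and one control, each open or closed, with KB103 given only to an open KB103 area. The second sentence of 6.5 can mean that neither KB103 area is dosed (lenient) or that not both are dosed (literal).

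| KB103 areas | Vehicle, lenient | Vehicle, literal |
|---|---|---|
| both open | given | given |
| one open, one closed | given | withheld |
| both closed | withheld | withheld |

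Each row is the same whether the control is open or closed. An open control therefore loses vehicle under both readings once both KB103 areas have closed. Under the literal reading it loses vehicle as soon as the first closes, while the other is still dosed. That reading contradicts the preceding sentence of 6.5. A closed control, conversely, keeps receiving vehicle while both KB103 areas are open. With one KB103 area the clause has no defined meaning.

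**2. Worst-case dose count.**

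Inputs from the documents:
- Dosing every 2 or 3 days for at most three months per cycle (Protocol 4.1), taken here as 90 days, with the first dose on Day 1.
- Closure times from Protocol 1.6: "Wounds that were chronic but recurring based on natural history tended to heal and close completely within 7 to 10 days of KB103 administration". These were seen under version 2, with daily dosing for 5 days.
- Assessments at Weeks 8, 10 and 12, taken as Days 56, 70 and 84.

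Assumptions: the same closure times hold under version 4.0, the control is still open, and no Cycle 2 dosing starts before Week 12.

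Full cycle:
- Every 3 days (Days 1, 4, ..., 88): (88 − 1)/3 + 1 = 30 doses.
- Every 2 days (Days 1, 3, ..., 89): (89 − 1)/2 + 1 = 45 doses.

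Days off vehicle = assessment day − last dose day.

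| KB103 closes | Interval | Vehicle doses | Last dose | Days off at Week 8 / 10 / 12 |
|---|---|---|---|---|
| Day 7 | 3 days | 3 of 30 (10%) | Day 7 | 49 / 63 / 77 |
| Day 7 | 2 days | 4 of 45 (9%) | Day 7 | 49 / 63 / 77 |
| Day 10 | 3 days | 4 of 30 (13%) | Day 10 | 46 / 60 / 74 |
| Day 10 | 2 days | 5 of 45 (11%) | Day 9 | 47 / 61 / 75 |

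Slower closure shrinks the loss. With closure at Day 28 (assumed), the control gets 10 of 30 or 14 of 45 doses (31% to 33%). With closure at Day 56 (assumed), it gets 19 of 30 or 28 of 45 (62% to 63%). If a KB103 area stays open for all 90 days, nothing is lost on the lenient reading.

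The literal reading adds a direct imbalance. Section 1.6 reports that wounds open for years "showed signs of healing following an initial five consecutive applications but the wound healing process appears to stagnate". A subject with one recurring and one stagnating KB103 area could receive 30 to 45 doses on the second area and 3 to 5 on the control.

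**Reach.** Version 4.0 plans 3 subjects of up to 14 in total: 3/14 = 21%. The SAP Overview reports 12 treated, of whom 2 + 4 + 5 = 11 are listed under earlier versions. That implies 12 − 11 = 1 under version 4.0 so far, or 1/12 = 8%.

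**The case against.** The strongest reply is that *target wound* in 6.4 includes the control. Protocol 6.3 treats all selected areas as target areas, and 10.3.2 names a placebo target wound. On that usage an open control could keep KB103 dosing going, and vehicle with it. Against this, 4.3 contrasts the target wound with the control wound. The text is mixed, so a reader may infer that 6.5 certainly deprives an open control of vehicle, and the documents do not support that much. The wide reading has its own cost: KB103 would go onto areas already closed, which blurs duration of closure, itself a primary objective.

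Three other points stand in part:

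- **Restart.** One might infer that vehicle resumes only when a KB103 area re-opens. Section 4.1 says so, but 5.5 does not name the area, so an enlarging control might start Cycle 2. The days off vehicle above are therefore a worst case, the more so because the 7 to 10 day figure comes from recurring wounds that may re-open.
- **Order of closure.** One might argue that vehicle stops only after KB103 has closed, so that which wound closes first is already settled. SAP 8.1.2 requires at least 90% reduction for 2 consecutive weeks. A KB103 wound that closes visibly, stops dosing and re-opens has not met it.
- **Yoked dosing.** Matching application days across wounds is a legitimate design. The protocol does not give it as a reason, though. The literal reading defeats it, and 4.1 and 6 describe dosing until closure.

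It is also fair that the SAP lists all eCRF data, so recorded dosing dates can be inspected, and that this is a pilot without a sample size calculation.

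**Conclusion.** The point holds as a defect in the dosing rule with a possible, unquantified bias. Section 6.5 ignores the control's state under every reading of its second sentence. It cannot be applied with one KB103 area, and its literal wording contradicts the sentence before it. Whether an open control actually loses vehicle depends on how 6.4 is read, and when vehicle resumes depends on whether 4.1 or 5.5 governs.

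A reader might conclude that the placebo results are biased toward KB103. The documents do not show that: they give no vehicle effect and do not say how often a control was left open. The direction is toward KB103 only if vehicle helps healing. The worst case is 3 to 5 doses instead of 30 to 45, with 46 to 49 days off vehicle at Week 8 and 74 to 77 at Week 12. It needs early KB103 closure, an open control and no Cycle 2 dosing before Week 12. Reach is at most 3 subjects, and apparently 1 of the 12 treated so far. Severity: minor to should-fix.

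**What to change.** Replace the 6.5 rule with one symmetric rule, used also in 4.1, 5.5, 5.7.1, 6 and 6.4: *Each area, KB103 or placebo, is dosed every 2 to 3 days until all wounds in that area are closed, 3 months elapse in that cycle, a stopping criterion is met or the Investigator stops dosing, regardless of the other areas.*

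Also state:

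- that a control may still be in Cycle 1 dosing when the KB103 areas enter OP 1;
- which area triggers Cycle 2;
- that a new 3-month limit starts for all areas when Cycle 2 begins.

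Add a placebo step to Appendix 1. For subjects already dosed, tabulate the number of doses and last dose date per wound against the closure date of the paired wound.

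The cost is protocol wording, one Appendix 1 step and one table from data already to be listed. The downside is extra gel on an open control. After early KB103 closure this is 30 − 4 = 26 to 45 − 4 = 41 more applications per cycle, at bandage changes that already take place. Application days would also no longer be matched between wounds, which the report should say.

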## **6.6 Peri- and Post-procedural Safety Monitoring**

Throughout the study, subjects will have full access to the care provided by Stanford's EB team. During visits to the clinic, subjects will be within 3 miles of the site. Throughout the study, subjects will have direct access to the PI via the PI's cell phone.

## **6.7 Post-Dose Procedures**

Following dosing, all empty or partially used vials will be destroyed per Stanford standard operating procedures. During the period in which KB103 and placebo is administered to the skin, patients should avoid touching, scratching, or tampering with the administration sites or their dressings. Following removal of KB103 and placebo, patients should minimize contact with the area. Bandages removed at home should be disposed of as outlined in Appendix 1.

## 7 Efficacy Evaluations

### 7.1 Wound Measurement

Prior to the first administration of IP, small tattoos are placed on non-blistered skin near the target wound for the purpose of locating the wound areas at subsequent visits.

#### 7.1.1 Imaging

Target wounds are measured at each visit to the clinic using a phone camera app. Investigators use the camera's software to define wound surface area and other measurements.

Target wounds are also monitored at home using the phone camera app. Subjects are instructed to image the target wounds during bandage changes (approximately twice per week).

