## 6      **Investigational Product**

Subjects are administered topical KB103 to one or two wound areas, and topical placebo to a second wound area. Wound areas have a surface area of up to 50 cm^2.

During Cycles 1 and 2, topical KB103 and placebo are administered every two to three days to coincide with bandage changes. Administrations continue until the wound closes, a stopping criterion occurs or at the discretion of the Investigator, not to exceed 3 months per cycle. After the first administration of each cycle, administrations can be administered at home by a trained caretaker at the discretion of the Investigator. These are referred to as "At-Home Topical Administrations" below. During visits to the Investigative site, KB103 may be administered topically by the Investigator. KB103 is prepared according to the pharmacy manual prior to administration.

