### **6.3      Wound Area Selection**

Up to three wound areas are selected to be part of the study: one or two to receive KB103, and one to receive placebo. Final selection of the wound areas occurs at baseline. The following is considered when selecting target wound areas:

- **Wound areas can consist of one wound, or multiple wounds, and can include intact skin.**
- **The size of the wound area.** Target wound areas have a surface area up to 50 cm^2.
- **The location of the wound area.** Appropriate sites are on the anterior and/or lateral trunk and/or upper and/or lower extremities in areas protected from frequent trauma or injury. Excluded areas include the face, and areas close to mucous membranes (genitourinary, oral or anal mucosa).

- **The appearance of the wound.** Wounds should appear clean with adequate granulation tissue, excellent vascularization, and not appear infected.
- **Historical consistency in size of the wound.** A wound with a historically more consistent surface area is chosen over a less consistently sized wound.
- **The similarity of the wounds.** To the extent possible, similarity in location on the body should be considered.
- Wounds that have previously been administered investigational gene or cell therapy (except for previous KB103 administration) are not eligible for KB103 and placebo administration.

The Investigator will first selection two areas; one for KB103 and one for placebo. If another area meets the criteria above, it will be considered for inclusion in the study to receive KB103.

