## 10.5 Proof of Mechanism Analyses

### 10.5.1 Expression of Collagen VII

Biopsies collected for the purpose of IF are evaluated for expression of collagen VII by a qualified reader.

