EB	epidermolysis bullosa
FDA	Food and Drug Administration
HEENT	head, ears, eyes, nose, throat
HSV	herpes simplex virus
IEM	immunoelectron microscopy
IND	Investigational New Drug application
ITT	Intent-to-treat
LTFU	long-term follow-up
MCH	mean corpuscular hemoglobin
MCHC	mean corpuscular hemoglobin concentration
MCV	mean cell volume
NC1	noncollagenous 1 domain
NC2	noncollagenous 2 domain
PP	per protocol
RBC	red blood cell count
RDW	red blood cell distribution width
SAE	serious adverse event
SD	standard deviation
WBC	white blood cell

1 Introduction

This document presents the Statistical Analysis Plan (SAP) for the protocol KB103-001, “A Phase I/II Study of KB103, a Non-Integrating, Replication-Incompetent HSV Vector Expressing the Human Collagen VII Protein, for the Treatment of Dystrophic Epidermolysis Bullosa (DEB).” The statistical plan described is prepared after an initial partial analysis was performed as the study is not a blinded study. This SAP summarizes the study design and objectives and provides details of the outcome definitions and statistical methods that will be used to completely analyze the data from Phase I through Phase II.

2 Study Objectives

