The efficacy objective is the proportion of DEB wound sites with complete wound healing from baseline ($\geq 90\%$ reduction in wound surface from baseline) in KB103 versus placebo treated intra-participant wound sites at Weeks 8, 10 and 12 as determined by the Investigator.

The number and percentage of subjects in each treatment group defined as Complete Wound Healing (CWH) will be tabulated. The null and alternative hypotheses are as follows:

Null Hypothesis $H_0: \%CWH \text{ in KB103} = \%CWH \text{ in Placebo}$

Alternate Hypothesis $H_1: \%CWH \text{ in KB103} > \%CWH \text{ in Placebo}$

Where $\%CWH$ is the percentage of wounds with a complete wound healing from baseline at week 8, 10 and 12. A one-sided significance level of 0.05 is considered

The objective of the proportion of DEB wound sites with complete wound healing from baseline ($\geq 90\%$ reduction in wound surface from baseline) will be analyzed using the Cochran-Mantel-Haenszel (CMH) test stratified by the time points (weeks 8, 10 and 12). Under the null hypothesis of no association between complete wound healing and treatment, this test statistic follows a chi-square distribution with 1 degree of freedom. The CMH test provides test of independence for the repeated evaluations at weeks 8, 10 and 12.

In addition to testing the null hypothesis, the CMH test also provides an estimate of the common odds ratio to summarize how large the treatment effect is when pooled across the different weeks of the treatment assuming the odds ratio is the same in the different weeks of treatment. This assumption will be tested using the Breslow-Day test and corresponding p-values will be provided. The null hypothesis of the CMH test is that the odds ratios within each week are equal to 1, indicating the complete wound healing proportions are the same.

A summary table with individual treatment proportions and the p-values treatment effect resulting from the chi-square test will be provided. In addition, p-values for independence of weekly evaluations (weeks 8, 10 and 12) using the Breslow-Day test will be provided.

8.1.1.1 Sensitivity and Supplemental Analyses of the Change in Wound Surface Area:

- The analysis performed in Section 8.1.1 for the efficacy objective will be repeated for the PP and LOCF imputed ITT populations.

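### Wound area, on which every wound outcome rests, is read from images by investigators who know the allocation, and no masked reading is planned

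*Protocol*

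**What the plan says.** **Who measures area.** Protocol 7.1.1 has target wounds measured at clinic visits with a phone camera app: "Investigators use the camera's software to define wound surface area and other measurements". Protocol 10.5.3 draws the area data from both on-site and at-home images. Who measures the at-home images is not stated, but Protocol 6.1 has the Investigator use them for remote dosing decisions.

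**Who decides healing.** SAP 8.1.1 compares KB103 with "placebo treated intra-participant wound sites at Weeks 8, 10 and 12 as determined by the Investigator".

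**What that person knows.** The SAP introduction states: "The statistical plan described is prepared after an initial partial analysis was performed as the study is not a blinded study". Protocol 6.3 says: "The Investigator will first selection two areas; one for KB103 and one for placebo". Protocol 6 adds: "During visits to the Investigative site, KB103 may be administered topically by the Investigator". Under Protocol 6.5, placebo is given only on days when KB103 is given, so whoever directs dosing must know the labels.

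**Biopsies.** Under Protocol 10.5.1, IF samples "are evaluated for expression of collagen VII by a qualified reader"; 10.5.2 uses the same kind of reader for IEM. Protocol 7.2 has IF processed at the site and IEM shipped to an outside laboratory. Coding of specimens is not described.

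**Safeguards.** The only rule separating assessors is in Protocol 7.4: a physician who administers the PROs may not also score the IGA. That rule does not conceal treatment.

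**The concern.** Deciding where a healing wound ends involves some judgement, and here the person judging knows which area had the active product. A reader who expects KB103 to work may, without intending it, draw a KB103 border tighter or a placebo border wider. The two readings are then subtracted or compared within the same patient, so a reading difference between treatments goes straight into the estimated effect.

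At stake is the main efficacy comparison. The SAP tests for superiority, and Protocol 1.6 says version 4.0 is meant to inform the Phase 3 trial. No later analysis can remove the bias, because every planned analysis uses the same readings.

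**Working it through.** There is no plan figure to reproduce: the documents give no sample size calculation, tracing error or expected distribution of reductions. The check is first a reading of which outcomes depend on the area, then an illustration of scale.

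**1. Outcomes that depend on the area reading**

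| Outcome | Where | Use of area |
|---|---|---|
| Change in surface area | Protocol 2.1 (1a), 10.5.3 | Continuous, paired t-test |
| Complete healing | SAP 8.1.1 | At least 90% reduction |
| Reductions of 50%, 75%, 100%; percent reduction | SAP 8.1.1.1 | Same areas, other cut-offs or continuous |
| Time to closure | SAP 8.1.2 | 90% line held for 2 consecutive weeks |
| Duration of closure | SAP 8.1.3 | Until reduction falls below 90% |

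The per-protocol, LOCF and other cut-off analyses change the subjects, the imputation or the threshold. None changes the reader, so none can show reader bias.

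**2. Continuous outcome.** Let Δ be the true mean KB103-placebo difference in change and δ the systematic reading difference between treatments. The expected observed difference is Δ + δ. Adding subjects narrows the interval around Δ + δ; it does not reduce δ.

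**3. Scale at the SAP's 90% line.** SAP section 3 gives sizes up to 10, 20 and 50 cm². At those maxima the line falls at 0.10 × 10 = 1 cm², 0.10 × 20 = 2 cm² and 0.10 × 50 = 5 cm² remaining. Under version 4.0 the 50 cm² area may include intact skin, so the residual for a wound inside it can be smaller. On a 20 cm² wound, an assumed 3-point tracing difference is 0.03 × 20 = 0.6 cm².

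**4. Wound counts (SAP section 3 table).** One placebo wound per patient. KB103 wounds: 2 × 1 for version 1.0, 4 × 2 for version 2.2 and 5 × 2 for version 3.1, then two per version 4.0 patient (assumed; the protocol allows one or two).
- 12 patients, as in the SAP text (one under version 4.0): 2 + 8 + 10 + 2 = 22 KB103, 12 placebo.
- 14 patients, the sum of the table rows: 2 + 8 + 10 + 6 = 26 KB103, 14 placebo.

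One reclassified placebo wound moves the placebo rate by 1/12 = 8.3 or 1/14 = 7.1 points.

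**5. False-positive illustration.** Assume no true effect, a healing rate p in both groups, and reading that raises the KB103 rate to p + b. With n_P placebo and n_K KB103 wounds, and p̄ the weighted mean rate:

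rejection rate = Φ[(b − 1.645·SE₀)/SE₁], where SE₀ = √[p̄(1−p̄)(1/n_P + 1/n_K)] and SE₁ = √[p(1−p)/n_P + (p+b)(1−p−b)/n_K].

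Example with n_P = 12, n_K = 22, p = 0.30, b = 0.10:
- p̄ = (12 × 0.30 + 22 × 0.40)/34 = 0.365
- SE₀ = 0.173; SE₁ = √(0.21/12 + 0.24/22) = 0.169
- Φ[(0.10 − 1.645 × 0.173)/0.169] ≈ 0.137

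| Shift b (assumed) | 12 placebo / 22 KB103 | 14 placebo / 26 KB103 |
|---|---|---|
| 0 | 5% | 5% |
| 5 points | about 9% | about 9% |
| 10 points | about 14% | about 15% |
| 20 points | 29–31% | 33–35% |

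Ranges cover p from 0.30 to 0.50. The calculation treats wounds as independent, uses one time point and a normal approximation in small samples. It does not model the SAP's test stratified over weeks 8, 10 and 12.

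**The case against.** **Recognition would defeat the coding.** This is the strongest objection. There is one site and at most 14 subjects, locating tattoos sit near the wounds, and the readers are investigators who chose the areas and may have dosed them. An initial partial analysis has also been done. This stands as a limit on the remedy. It does not justify leaving the label in view.

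**There are other protections.** Stencil tracings are kept on file (Protocol 7.1.2), the SAP adds other cut-offs and a continuous comparison, and it describes the design as randomised. The stencils are a second record, but no masking is described for them either. The other cut-offs reuse the same areas. Randomisation, where it was done, does not hide the label from the reader.

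**Reading may be largely automatic.** Protocol 7.1.1 does not say how much of the border the software sets. That is fair: it limits what can be said about size, but the measurement remains the investigators' to define.

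**Stronger readings that the documents do not support:**
- *That the biopsy readers know the treatment.* The documents say only that readers are qualified, and IEM goes to an outside laboratory. An unblinded study does not settle what a laboratory reader sees. Masking is simply not specified. In Phase II, IF and IEM are listed under other objectives, biopsies are optional, and SAP 8.2 plans no formal test. They were primary only in Phase I, with two patients.
- *That every primary objective turns on the 90% line.* That line is only in the SAP. Protocol objective 1a is continuous. What the outcomes share is the area reading.
- *That coding costs no staff effort.* Someone other than the reader must hold the code, and the documents are silent on staffing and on image archiving.

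**Conclusion.** The concern holds for wound area. The documents together show that area is read, and healing determined, by investigators who know the allocation, with no masked reading provided for. This may bias change in area, healing rates, time to closure and duration, and the planned sensitivity analyses cannot reveal it. The point should be acted on.

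The size is unknown. The rejection rates above are illustrations that rest on assumed shifts, healing rates and independent wounds; they are not estimates for this trial. A reader might infer that the results are in fact biased towards KB103, but the documents give no tracing error, repeat readings or distribution of reductions from which to show that.

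For IF and IEM the finding is only that masking is unspecified, which is minor given their role in Phase II.

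**What to change.** **Protocol 7.1.1 and SAP 8.1.1.** In the SAP, replace the words "as determined by the Investigator". State in both documents that:
- endpoint areas come from stored images, on-site and at-home, exported under a random code by an existing staff member who does not trace;
- treatment label and date are removed and images are presented in random order;
- the existing investigators trace them, and results are entered before the code is opened;
- live tracings used for care are kept separate and do not supply endpoint data;
- stored images from earlier protocol versions either are, or are not, re-read in the same way.

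Both documents need the change; if only the protocol is amended, the SAP endpoint still rests on the unmasked determination.

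**Minor addition, Protocol 7.2 and 10.5.1–10.5.2.** Label IF and IEM specimens with codes that hide treatment and visit until results are entered.

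**Cost.** Coding work and a second tracing pass by existing staff, with no change to treatment or visits. It assumes that the app's images are retained, which the documents do not state. Masking remains partial, because an investigator may recognise a body site or tattoo, and the report should say so.
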